3. METHODS AND ASSESSMENTS

3.1 Schedule of delivery of intervention and data collection

Table 1 describes the trial assessments and timepoints for data collection.

Visit	1	2	3	4	5	6
Visit Window (No. Weeks \pm No. Days)	Baseline	Hospital stay	At discharge	30 days (\pm 14 days)	90 days (\pm 28 days)	180 days (\pm 28 days)
Informed consent	✓*	✓*				
Medical history	✓					
Inclusion/exclusion criteria	✓					
Intervention	✓					
FIM (motor and cognition)		✓	✓	✓		✓
ASIA neurological scale		✓	✓			
Intercranial hypertension		✓				
Length of stay			✓			
Further treatment for c-spine injury			✓	✓		
Cost and resource utilisation			✓	✓		✓
Quality of Life (EQ-5D-5L/EQ-5D-Y)		✓	✓	✓		✓
Adverse events	✓	✓	✓			
Survival status				✓	✓	✓

*Due to the emergency nature of the trial, participants will be enrolled in the trial prior to consent. Once participants have recovered sufficiently (usually around the time of discharge from the Intensive Care Unit) and whilst they are still in hospital, a member of the hospital research team will approach the patient (or if they lack capacity a consultee) to explain the trial and seek consent to continue in the trial

3.2 Data Collection

3.2.1 Participant enrolment

The randomisation PWA will collect the following identifiable data e.g.

- Date/time of injury
- Date/time received in hospital
- Initials
- Hospital number
- CAD/EPR number
- Neurological impairment
- Analgesia given (pre-hospital)

7.2.2 Baseline

The following data will be collected at the time of hospital admission by the ambulance service/hospital research team;

- Gender
- Age
- Neurological impairment
- Duration of immobilisation (up until arrival at hospital)
- Mechanism of injury (e.g. road traffic accident/push bike/fall/sports injury/assault)

3.2.2 In hospital

The following data will be collected in hospital. These data will include:

- Duration of immobilisation in hospital
- Analgesia given (in hospital)
- CT scan appearance
- Details of cervical spine injury
- Mortality
- Evidence of infection
- The length of ICU stay and level of stay
- The length of hospital stay (dates)
- Interventions used for c-spine injury in the hospital and up to discharge
- Discharge destination
- Adverse events (e.g. chest infections, pressure sores, raised ICP)
- Other injuries sustained (randomisation to discharge)
- Injury Severity Score

The following will be collected as close as possible to the point of admission and discharge

- FIM (total and sub-scales)
- ASIA neurological scale
- Variables that will assist in the health economics analysis (including EQ-5D-5L/EQ-5D-Y).

If participants are discharged from the emergency department before a member of the local research team has had the opportunity to collect this data, their FIM-motor score will be recorded as 7 (total independence).

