1. BACKGROUND

1.1 Existing knowledge

NHS Ambulances use cervical collars for spinal immobilisation in large numbers of “at risk” injured patients (~ 80,000/year in UK, 5 million/ year in USA¹) but the numbers of patients shown to have a significant cervical vertebrae or spinal cord injury (SCI) is much less; 5476 in 2017 (from national major trauma registry, Trauma Audit & Research Network- TARN) with just under one third having cervical SCI (n=1376). A large number of patients are immobilised due to the challenges, even using the NICE decision rule, to confidently rule out unstable cervical spine (c-spine) fractures. Most civilian trauma is “blunt” (falls and road traffic collisions), where precise injury assessment is not possible in unconscious patients and difficult in conscious patients, who may have whiplash muscle injury, and may initially appear similar to a patient with an unstable spinal fracture. This means that at least 75% of patients exposed to the discomfort and complications of spinal immobilisation have no potential benefit. In the majority of immobilised patients, injuries to the spine are ruled out by assessment or imaging in the emergency department (ED) which allows removal of immobilisation within hours; however, ruling out an unstable spinal fracture may take much longer in comatose patients with brain injuries. Previous reports suggested that after imaging, 2-4% of major trauma patients have a significant c-spine injury. A published study using TARN data from 1998-2009 shows 2.3% of major trauma patients had a significant c-spine fracture or dislocation and 0.8% had a cervical SCI diagnosed prior to hospital discharge². The expansion of TARN to all trauma-receiving hospitals and better access to imaging has seen the average age of major trauma patients increase considerably in the intervening decade (current TARN median age = 59 years). The most recent analysis in 2017 suggests the true prevalence of significant potentially unstable c-spine injury and SCI within major trauma patients is therefore more than double (6% & 1.8% respectively). In the older population, cord contusion without fracture (e.g. central cord syndrome) is also more common. Recruitment will occur across the UK ensuring areas with a high disease burden make a substantive contribution.

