2.3 Outcome measures

FIM: The primary outcome for the trial is the Functional Independence Measurement (motor) (FIM-motor). The FIM was developed as a functional assessment measure for all diagnoses in the rehabilitation setting and has been used to assess outcome in trauma populations away from the rehabilitation setting¹². The FIM consists of 18 items across 6 domains: self-care; sphincter control; mobility; locomotion; communication; and social cognition. There are 13 items related to motor activities and 5 assessing cognitive function. Each item rates the patient's level of disability on a scale from 1 to 7, with 1 representing total dependence and 7 describing complete independence without the need for an aid. Performance on each item is summed to form the FIM total score, which ranges from 18 (lowest function) to 126 (highest function). There are 2 additional sub-scores. The FIM cognitive score uses the 5 cognitive items to create a score from 5 (lowest cognitive function) to 35 (highest cognitive function). The FIM motor score sums the patient's performance on each of the motor items and ranges from 13 (lowest motor function) to 91 (highest motor function). The FIM motor score at discharge has also been found to be a significant independent predictor of return to work or study¹². Moreover, FIM motor reflects well the functional status of individuals following traumatic spinal cord injury¹³.

ASIA Impairment Scale¹⁴: The American Spinal Injury Association Impairment Scale (ASIA) is a standardized neurological examination used by the rehabilitation team to assess the sensory and

motor levels which were affected by the spinal cord injury. The scale has five classification levels, ranging from complete loss of neural function in the affected area to completely normal. Neurological deterioration is defined as the change from 'E' – normal to 'A-D' – impairment.

EQ-5D-5L¹⁵: The descriptive system comprises five dimensions: mobility, self-care, usual activities, pain/discomfort and anxiety/depression. Each dimension has 5 levels: no problems, slight problems, moderate problems, severe problems and extreme problems. The patient is asked to indicate his/her health state by ticking the box next to the most appropriate statement in each of the five dimensions.

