2.3.1 Effectiveness

Primary effectiveness outcome:

- Total Functional Independence Measurement motor (FIM-motor) score at discharge. The FIM is an 18-item instrument measuring a person's level of disability in terms of burden of care. The FIM should be rated by the consensus opinion of a multidisciplinary team, but the evaluation is often performed by a single professional.

Secondary effectiveness outcomes:

- FIM-motor at 30 days, 180 days after randomisation at video clinic or follow up appointment;
- FIM-total and cognition scales at discharge, 30 days and 180-day at video clinic or follow up appointment;
- ASIA Impairment Scale at discharge;
- Mortality (at days 30, 90 and 180);
- Intervention for c-spine injury in the first 30 days or discharge (use of collar for > 2 weeks, halo brace, c-spine surgery);
- Discharge destination;
- Pre-hospital analgesic requirements (from Ambulance PRF).

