2.7.4 Approaching patients or their consultee following discharge

In rare circumstances, participant (or appropriate adult for children/young people who lack competence) consent or a personal/professional consultee opinion may not be obtained before hospital discharge.

If this occurs, the hospital or ambulance (if taken to a non-participating hospital) research team will contact the participant (or appropriate adult for children/young people who lack competence) or their consultee (if it is known that the participant lacks mental capacity) to seek consent or an opinion. Up to 3 contact attempts will be made within 14 days of discharge. The researcher will use available systems to determine correct contact information and, where appropriate, to ensure the participant is still alive. Where available, more than one system will be accessed to determine survival status.

If the participant (or appropriate adult for children/young people who lack competence) or their consultee does not respond, non-identifiable data which have already been collected will be retained, and no further data collection will continue.

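### Participants who leave the ED before a researcher reaches them are recorded as fully independent on the primary outcome without any check of function, and the planned missing-data analysis does not test those scores.

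*Protocol*

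**What the plan says.** The primary outcome in protocol 2.3.1 is the "Total Functional Independence Measurement motor (FIM-motor) score at discharge". Section 3.2.2 asks for FIM as close as possible to admission and discharge, and then makes one exception. It covers participants "discharged from the emergency department before a member of the local research team has had the opportunity to collect this data". The instruction for this group is that "their FIM-motor score will be recorded as 7 (total independence"). The sentence sets no other condition: no clinician rating, record review or functional criterion.

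Section 2.3 says that the motor score "ranges from 13 (lowest motor function) to 91 (highest motor function"), and that each item is rated from 1 to 7, "with 1 representing total dependence and 7 describing complete independence without the need for an aid".

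Section 6.2.1 declares non-inferiority if the lower 95% confidence bound does not pass -2. It adds an exploratory multiple imputation for missing FIM-motor outcomes.

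On how many participants the rule might reach, section 1.1 says only: "In the majority of immobilised patients, injuries to the spine are ruled out by assessment or imaging in the emergency department (ED"). Section 2.7.4 covers participants who leave hospital before consent: "Up to 3 contact attempts will be made within 14 days of discharge".

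**The concern.** Take two participants with the same function, both sent home from the ED. The one a researcher reached gets a measured score. The other gets full independence. For the second, the primary endpoint records whether staff arrived in time.

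Full independence will not be true of everyone sent home. The trial takes all ages, including under-16s, and full marks require independence without an aid. A participant who uses a walking aid, was dependent before the injury, is a very young child or has a new limb injury would score lower. Section 1.1 gives a "current TARN median age = 59 years" for major trauma, which shows that older patients are common but does not measure dependence.

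Time in the ED comes after randomisation, the trial is open-label, and one arm arrives in collar, blocks and tape while the other may sit up. Equal default rates are therefore not guaranteed. What is at stake is a test with a 2-point margin, for which small systematic shifts matter.

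**Working it through.** **Inputs from the protocol (6.1, 6.2.1, 2.3).** Margin 2; SD 25.93; one-sided 2.5%; power 90%; loss 15%; 13 motor items rated 1 to 7, total 13 to 91.

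**The plan's own figure.** n per arm = 2 × (1.960 + 1.282)² × 25.93² / 2² = 3,533. Dividing by 0.85 gives 4,157 per arm, 8,314 in total, against 8,316 stated. The sample size reproduces and is not at issue.

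**Planned standard error.** SE = 25.93 × √(2/3,533) = 0.617.

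**Value of the default.** Seven on each of 13 items is 13 × 7 = 91, which fits the words for total independence. A motor total of 7 lies below the minimum of 13. The rest of this working takes 91.

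**Effect on the comparison.** Let p be the share of an arm that is defaulted and g the gap between 91 and the true mean of those defaulted. The recorded arm mean exceeds the true mean by p × g, so

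shift in the difference = p(intervention) × g(intervention) − p(control) × g(control).

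*Case A: unequal rates, equal gap.* Shift = d × g, where d is the difference in shares. The chance of declaring non-inferiority at a true difference of -2 is Φ(shift/0.617 − 1.960). The protocol gives neither d nor g; the values below are assumptions.

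| d | g | Shift (points) | False non-inferiority |
|---|---|---|---|
| 0 | any | 0 | 2.5% |
| 2 pp | 5 | 0.10 | 3.6% |
| 2 pp | 20 | 0.40 | Φ(−1.312) = 9.5% |
| 15 pp | 5 | 0.75 | Φ(−0.744) = 22.8% |

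The sign can equally be negative. With a shift of −0.75 and a true difference of 0, power falls from 90% to Φ((2 − 0.75)/0.617 − 1.960) = Φ(0.066) = 53%.

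*Case B: equal rates.* If a share p is set to 91 in both arms and a deficit of -2 applies to everyone, the recorded difference is -2 × (1 − p): -1.5 at p = 25%, -1.0 at 50%, -0.5 at 75%. These shares are also assumptions. Without a true difference among the defaulted patients, the difference is not attenuated.

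**Does the plan test this?** The imputation in 6.2.1 replaces missing scores. A defaulted score is present in the data and passes through unchanged. FIM is also scheduled at 30 and 180 days, but 3.2.2 does not use those ratings to check or replace the default.

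**The case against.** The rule covers only ED discharges whom researchers did not reach. A reader might infer that the primary score as a whole follows ED stay, or that the arm with faster ED discharge will gain points. The documents support neither. The upward direction needs the default to mean 91; a literal 7 would reverse it, lowering an arm's mean by 0.84 points per percentage point defaulted if the true score is 91 (0.01 × 84). No section reports a difference in ED stay between the arms. Staff presence at a given time should be balanced by randomisation stratified by centre, and if staff are mostly absent, nearly all ED discharges are defaulted in both arms.

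A reader might also take section 1.1 to mean that most participants go home from the ED. It describes ruling out spinal injury there, not discharge. Section 6.1 points the other way, likening the trial population to a cohort with Injury Severity Score above 15. Many people sent home may truly be near 91, which makes the gap small.

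Finally, sensitivity analyses can be left to a statistical analysis plan, and length of stay, in-hospital immobilisation time and later FIM ratings would allow some checking.

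These arguments remove any claim about actual size or direction. They do not remove the defect. The protocol itself fixes the data-capture rule, and no later analysis plan can recover discharge scores that were never sought.

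**Conclusion.** The concern holds in limited form. For ED discharges not reached in time, section 3.2.2 assigns the best possible primary score on the basis of researcher timing, and the imputation in 6.2.1 does not test it. Read as 91, the default can bias the comparison in either direction if rates differ between arms. With equal rates it attenuates any true deficit among those defaulted, toward non-inferiority. It causes no bias if those patients truly score 91.

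The size is unknown. The 9.5% and 22.8% error rates illustrate how sensitive a 2-point margin is with an SE of 0.617; they are not estimates of bias in this trial. A shift as large as the margin would need, for example, 10 percentage points more defaults in one arm and a gap of 20 points (0.10 × 20 = 2.0), and nothing in the documents supports such inputs. The literal 7 is a separate error, to be reconciled with the 13 to 91 range in 2.3.

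**What to change.** (a) In 3.2.2, before any default is applied, seek FIM-motor at ED discharge from the treating clinician or the record, or at the contact within 14 days in 2.7.4. Participants who leave the ED unreached are the ones that contact is meant for. Flag every score that is still defaulted.

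(b) In 6.2.1, report the number of defaulted scores by arm. Repeat the primary analysis with defaulted scores set to missing in the planned multiple imputation, and again with the default value varied.

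Giving every ED discharge the maximum score would not be a remedy. It would overwrite measured scores, leave the value tied to a post-randomisation event, and enlarge the share pulled toward zero.

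The cost is slightly longer contact calls, some recalled rather than directly rated scores, and one additional sensitivity analysis. Non-responders without a usable record would still be defaulted, which is why the flag and the analysis in (b) are needed as well.

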6.2 Statistical analysis of efficacy and harms

6.2.1 Primary outcome analysis

For the primary analysis, the difference in the FIM-motor score (and 95%) confidence interval will be derived using unadjusted and adjusted (for important covariates) analyses, using the linear regression models. In terms of interpretation, the intervention would be said to be not unacceptably worse than (i.e., non-inferior to) the control if, when the 95% CI around the difference in the effect size between the interventions is calculated and the lower bound of the interval does not extend beyond the -2.

A further exploratory analysis to assess the impact of missing outcome data on FIM-motor score will be examined using multiple imputation techniques.

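### The rule for participants discharged early from the emergency department assigns a FIM-motor score of 7, which is the maximum of one item and impossible as a total on the 13 to 91 scale

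*Protocol*

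**What the plan says.** Protocol section 3.2.2 lists the FIM among the measures taken near admission and discharge. It then adds a rule for people who leave the emergency department before research staff can assess them: "their FIM-motor score will be recorded as 7 (total independence").

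Section 2.3 describes the instrument: "There are 13 items related to motor activities and 5 assessing cognitive function". Each item is rated from 1 to 7, "with 1 representing total dependence and 7 describing complete independence without the need for an aid". The motor score is the sum of the motor items and "ranges from 13 (lowest motor function) to 91 (highest motor function").

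Section 2.3.1 names the primary outcome: "Total Functional Independence Measurement motor (FIM-motor) score at discharge". Under section 6.2.1, "the difference in the FIM-motor score (and 95%) confidence interval will be derived using unadjusted and adjusted (for important covariates) analyses", using linear regression, and non-inferiority is judged against a lower limit of -2. Section 6.1 sets that margin at 2 points.

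No section converts the 7 of section 3.2.2 into a total.

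**The concern.** The number and its label disagree. On the scale in section 2.3, 7 means full independence on one item. As a FIM-motor total it lies outside the possible range, on the side of worst function, while the label says best function.

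This sentence fixes the value of the primary outcome for a whole class of participants. Staff or programmers who followed it literally would record the participants presumed to be independent as worse than totally dependent. The spread of the outcome would widen, and an arm with more early discharges would look worse for it.

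The class may not be small. Entry is open to anyone with blunt trauma who is judged to need immobilisation, at any coma score (section 2.4.1). Section 1.1 says that in most immobilised patients "injuries to the spine are ruled out by assessment or imaging in the emergency department (ED) which allows removal of immobilisation within hours". That does not give the share discharged unassessed, but it gives no reason to treat the group as negligible.

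**Working it through.** **Inputs.** 13 motor items, each rated 1 to 7 (section 2.3). Margin 2, SD 25.93, power 90%, two-sided 5%, loss 15%, 4158 per arm (section 6.1). Median 61 in the study that supplied the SD (section 6.1, item 3), used here as the mean of assessed participants.

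**Assumptions.** A share p of participants falls under the rule, equal in both arms unless stated. The protocol does not give p; 25%, 50% and 75% are illustrations. The rest have mean 61 and SD 25.93.

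**1. The planned size reproduces.** n per arm = 2 × (1.96 + 1.2816)² × 25.93² / 2² = 3532.4, so 3533. Dividing by 0.85 gives 4157 per arm, 8314 in total, against 8316 stated. The sample size is not in dispute. Analysed per arm: 4158 × 0.85 = 3534.

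**2. Scale limits.** Minimum 13 × 1 = 13; maximum 13 × 7 = 91. The assigned 7 is 13 - 7 = 6 below the minimum and 91 - 7 = 84 below the maximum. The error per affected participant is 84 / 2 = 42 times the margin.

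**3. Effect on SD and power.** With assigned value v:

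- variance = (1 - p) × 25.93² + p(1 - p) × (61 - v)²
- SE = SD × √(2/3534)
- power = Φ(2/SE - 1.96), at a true difference of zero

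| p | Variance, v = 7 | SD | Power | Variance, v = 91 | SD | Power |
|---|---|---|---|---|---|---|
| 0 | 672.4 | 25.93 | 90% | 672.4 | 25.93 | 90% |
| 25% | 504.3 + 546.75 | 32.4 | 74% | 504.3 + 168.75 | 25.9 | 90% |
| 50% | 336.2 + 729.0 | 32.6 | 73% | 336.2 + 225.0 | 23.7 | 94% |
| 75% | 168.1 + 546.75 | 26.7 | 88% | 168.1 + 168.75 | 18.4 | >99% |

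Coded 7, power is lost at every share shown. Coded 91, it is not.

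**4. Effect on direction.** If early discharge is one percentage point more frequent on the intervention, the arm difference moves by 0.01 × (7 - 61) = -0.54 points when coded 7, and by 0.01 × (91 - 61) = +0.30 when coded 91. A true difference of 2 / 0.54 = 3.7 percentage points would shift the coded-7 estimate by the whole margin, against the arm that sends more people home early.

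**5. Could chance alone do this?** At p = 50%, the SE of the difference in proportions is √(2 × 0.25 / 3534) = 0.0119, or 1.2 percentage points. A gap of 3.7 is about 3.1 SE, so chance is an unlikely cause, and chance variation is already in the inflated SD. The shift matters if the arms truly differ in early discharge.

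**The case against.** The strongest reply is that this is a slip of wording. The label and the item scale both point to 7 per item, a data manager would probably notice a total below 13, and nothing shows that the database would hold 7 as the total. This stands in part: steps 3 and 4 describe literal use of the rule, not what will happen. It does not remove the need to correct the sentence, which is the only instruction for these values.

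It is also fair that section 1.1 speaks of spinal injury being ruled out and immobilisation removed, not of discharge, and still less of discharge without assessment. The shares are therefore assumptions, and at 75% the loss of power is small.

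A reader might go further and infer that a corrected score of 91 biases the trial towards non-inferiority, because a constant adds no difference between arms and dilutes any deficit in the others. The documents do not support this. A constant gives zero difference only within the assigned records; unequal shares still move the overall estimate (step 4). If these participants really are at or near 91 in both arms, a smaller overall difference is the true effect in the broad population the trial enrols. Bias would need a real difference between arms among those assigned 91, and nothing in the protocol shows one.

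What remains is narrower. The score is triggered by not having been assessed, not by documented function, in a trial that takes all ages and records other injuries. Because the value is recorded, it would also escape the missing-data analysis in section 6.2.1.

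**Conclusion.** The contradiction between sections 3.2.2 and 2.3 is certain and needs no assumption. The value prescribed for the primary outcome is impossible on the protocol's own scale and runs opposite to its label. It must be corrected before it is used for data entry or analysis.

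The consequences are conditional on 7 being entered and analysed as the total, and their size on the assumed shares and the mean of 61. Under those conditions power falls from 90% to between 73% and 88%, and the estimate moves 0.54 points the wrong way per percentage point of true difference in early discharge.

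That assigned scores rest on absence of assessment is a secondary remark. No figure in the protocol sizes it, and it is not shown to bias the result.

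**What to change.** In section 3.2.2, replace the 7 with: 7 on each of the 13 motor items (FIM-motor total 91). Add a database check that any FIM-motor total lies between 13 and 91. The cost is one sentence in the protocol, the matching case report form wording and one validation rule.

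As a secondary step, flag every assigned score and repeat the primary analysis without them as a sensitivity analysis. This costs one data field and one extra analysis, whose details can sit in the SAP, which was not available here.

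Multiple imputation should not be the default replacement for the assigned score. Section 6.2.1 plans it only as exploratory, and a model fitted largely to assessed, sicker patients could pull early discharges well below their true function.
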